3.3 VISIT WINDOWS

In general, data for assessments that are collected by scheduled visits will be mapped to visits that appear in the schedule of assessments per the protocol using the actual study day of assessment. Data will not be mapped to visits for which the assessment was not scheduled in the protocol (i.e., results for an assessment conducted at an unscheduled visit will be mapped to the appropriate visit at which the assessment was scheduled).

Visit windows will be continuous from the midpoint between two consecutive study visits, and will be dependent on the Schedule of Assessments for each variable independently. Since patients start the SFU period at different times, the start day of SFU will be considered in defining the SFU visit windows (See [Table 1](#)).

Table 1 Time Windows in Study Days Assigned to the SFU Study Visit

Study Visit	Time Window (Days)
Start of SFU (BL _{SFU})	BL _{SFU}
Week 12	$\geq \text{BL}_{\text{SFU}}$ to $\leq \text{BL}_{\text{SFU}} + 126$
Week 24	$> \text{BL}_{\text{SFU}} + 126$ to $\leq \text{BL}_{\text{SFU}} + 210$
Week 36	$> \text{BL}_{\text{SFU}} + 210$ to $\leq \text{BL}_{\text{SFU}} + 294$
Week 48	$> \text{BL}_{\text{SFU}} + 294$ to $\leq \text{LPLV}$

LPLV=last patient last visit; SFU=safety follow-up.

Data displays that are presented by visit will be visits at which the assessment was scheduled to be collected. The methods for handling multiple values within a visit window are described in the Primary SAP.

3.4 ANALYSIS OF STUDY CONDUCT

The following analyses of study conduct will be carried out on the safety, intent-to-treat, modified intent-to-treat population (mITT) and rescue populations, as appropriate (See primary SAP, Section 4.1).

The number of patients who completed or discontinued from the study during the SFU period, including the reason for discontinuation, will be summarized by treatment group. A listing of early withdrawals will be produced.

Concomitant medications given for PV will be summarised descriptively by mapped term and treatment group.

Demographic and baseline disease characteristics will be summarized for patients who entered SFU, as described in the primary SAP, Section 4.1.

Summary statistics for duration of SFU period per treatment group will be produced. The duration of SFU period for a patient will be the duration from BL_{SFU} to the last available SFU assessment for that patient.

3.5 PHARMACOKINETIC AND PHARMACODYNAMIC ANALYSES

Serum rituximab concentrations will be listed by patient and nominal time of collection. Summary statistics of serum rituximab concentrations will be presented by nominal time of collection including n, mean, SD, coefficient of variation, geometric mean, median, and range.

3.6 SAFETY ANALYSES

The safety analysis will be performed on the safety population as defined in the primary SAP, Section 4.1.3, for patients who entered SFU.

Rescue patients entered SFU will be analyzed separately.

Rituximab—F. Hoffmann-La Roche Ltd
6/Statistical Analysis Plan WA29330

Serious adverse events (SAEs) and all infectious adverse events, irrespective of causality, will be analyzed in the SFU period. Pregnancy information will be reported for the duration of the SFU period.

3.6.1 Adverse Events

Adverse events (AEs) will be mapped and reported using the MedDRA thesaurus using the most current version at the time of analysis (version 17.1 or later). Glossaries showing the mapping of investigator verbatim terms to coded events will be produced.

AEs with observed or imputed onset date, on or after the start date of the SFU period, will be summarized and listed.

AEs will be summarized by system organ class (SOC) and preferred term (PT), and will be presented in order of descending frequency summed across the treatment arms within each SOC and PT.

Listings will show AEs reported, and highlight the telemedicine patients, the patients who received rescue therapy in the 52-week treatment period and the patients who received rituximab in the SFU period.

The following will be summarized, and/or listings produced where required:

- SAEs
- Infections
- Serious Infections
- Symptoms of Serious Infusion Related Reactions (IRRs)
- SAEs leading to withdrawal

3.6.2 Deaths

Details of any deaths will be presented in an individual patient listing.

3.6.3 Laboratory Data

3.6.3.1 Immunoglobulins

The absolute values will be summarized by treatment group and visit for total immunoglobulin (Ig), IgA, IgG, and IgM.

The proportion of patients with a value of IgA, IgG, and IgM which is less than the lower limit of normal at each visit will be produced. Plot of mean and median IgA, IgG and IgM will be produced.

3.6.3.2 Lymphocyte Populations

The following natural killer (NK) cells, T, and B lymphocytes will be analyzed via flow cytometry:

- CD19

Rituximab—F. Hoffmann-La Roche Ltd
7/Statistical Analysis Plan WA29330

- CD3
- CD4
- CD8
- Naïve B cells (CD19+ CD27–)
- Transitional B cells (CD24^{high}CD38^{high})
- Memory B cells (CD19+CD27+)
- NK cells (CD56+)

The absolute values will be summarized by visit and treatment group for the above lymphocyte populations.

The proportion of patients with a lymphocyte value less than the lower limit of normal by visit and treatment group will be produced for the following lymphocytes:

- CD3
- CD4
- CD8
- CD19

3.6.3.3 Desmoglein-1 and Desmoglein-3 Autoantibody Titers

Summary statistics for anti-desmoglein–1 (Dsg-1) and anti-Dsg-3 titers during the SFU period will be produced by treatment group. A listing of anti-Dsg-1 and anti-Dsg-3 titers will be produced.

3.6.3.4 Anti-Drug Antibodies

The proportion of patients that are ADA (anti-drug antibodies [referred to as HACA in the protocol]) positive/negative at each visit will be summarized by treatment group. A listing of ADA results will be produced.

3.7 EXPLORATORY ANALYSES

The exploratory efficacy analysis will be performed on the mITT population as defined in primary SAP, Section 4.1.5.

3.7.1.1 Oral Corticosteroids

Oral corticosteroid exposure over the SFU period will be summarized by treatment group.

Oral corticosteroid use over time will be further investigated. Summaries will be generated which will include:

- Total cumulative dose per visit interval
- Total number of days on oral corticosteroids over the SFU period

The mean daily dose for a given visit interval will be calculated as follows:

sum of total daily dose across all days in the visit interval ÷ (end date of visit interval – start date of visit interval + 1).

All available data presented by specified visit intervals will be used; if a patient withdraws during a time interval, no imputation will be made for the remaining days in the interval, and available data up to the time of withdrawal will be used in the calculation.

A listing showing oral corticosteroid dosing for patients over the SFU period will be produced.

See primary SAP, Section 4.7.2.1 for Data Handling for Oral Corticosteroids

3.7.1.2 Pemphigus Disease Area Index

The absolute value of Pemphigus Disease Area Index (PDAI) activity score will be summarized by visit for each treatment arm.

The main method for handling missing PDAI data will be via imputation. Details of PDAI imputation methods are described in the primary SAP, Section 4.7.1.2.

3.7.1.3 Total Number of Flares

The total number of flares occurring during the SFU period will be summarized and analyzed as described in the primary SAP, Section 4.7.2.2.

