For reporting purposes, all relevant oral corticosteroid entries will be standardized by converting to a prednisone equivalent dose, and will be reported under the term 'Prednisone'. A listing of all compounds reported as prednisone will be produced along with the conversion factor applied.

The study management team will monitor oral corticosteroids on an ongoing basis for data quality and to ensure all dose adjustments are being correctly captured. All efforts

Rituximab—F. Hoffmann-La Roche Ltd
20/Statistical Analysis Plan WA29330

will be made to resolve missing or ambiguous data prior to database lock. In the case that data queries cannot be resolved, data will be handled in a conservative manner as described in the sections below.

The intervals for each dose of oral corticosteroid captured during the taper are expected to be continuous and non-overlapping. Patients who are adequately controlled by their blinded treatment may discontinue oral corticosteroids altogether, but may re-start treatment as required to treat any increases in disease activity. With this in mind, the use of available data will be maximized and incorporated into the imputation of missing or partial dates as follows:

Missing Term	Imputation Method
Start Date	
Missing Day	Latest of the following: Previous End Date+1 First day of the month
Missing Month	Previous End Date+1
Missing Year	No imputation
End Date	
Missing Day	Earliest of the following: Next Start Date-1 Last day of the month
Missing Month	Next Start Date-1
Missing Year	No imputation

Within two consecutive dosing intervals, if the end date of the first dose interval is missing and the start date of the second dose interval is missing, a midpoint approach using the start date of the first interval and the end date of the second interval will be used to assign a cut-off end date, providing these dates are available.

A missing or 'ongoing' final end date will be imputed with the exposure date. A missing initial start date will be imputed with Day 1 providing the end date is after Day 1, otherwise no imputation will be made.

If the total daily dose is missing then the dose will be imputed using the dose from the previous dose or the next dose, whichever is higher.

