4.7.2.2 Total Number of Flares

The total number of flares occurring during the treatment period will be evaluated by taking into account the number of flares experienced and the exposure period. Patient level flare and exposure data will then be aggregated, and the rate of flares compared between the RTX and MMF treatment groups. Rate of flare will be analyzed using a Poisson regression model with a log link and the log of each patient's duration in study as an offset variable. The model will include factors for treatment, region, duration of illness, baseline PDAI activity score, and baseline prednisone dose. The total number of flares, total exposure (weeks), and rate of flare will be presented by treatment group along with maximum likelihood estimates for the rate ratio, 95% confidence interval for the rate ratio, and p-value. A Pearson Chi-Square test will be used to assess over-dispersion of Poisson model. If an over-dispersion is detected based on this test, then a negative binomial model will be used. If the number of flares has an excess of zero counts according to the score test ([van den Broek, 1995](#)), a zero-inflated negative binomial model will be applied.

The exposure period for a patient will be the duration from Day 1 to the earliest of the following: early withdrawal, receipt of rescue, Week 52 visit.

Additional exploratory work may be undertaken to investigate the potential changes of flare rates over time, for example by assessing the number of flares over specified time intervals.

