4.9.1 Exposure to Study Medication

The number and percentage of patients who received RTX will be summarized by treatment course, along with summary statistics for the dose of RTX received at each infusion and overall.

Duration of rituximab exposure will be calculated as:

- exposure date – date of first rituximab infusion + 1 where exposure date is the earliest of the following:
 - Week 52 visit (using upper visit window of Day 364+10 days)
 - Date of early withdrawal

RTX exposure data will be determined using the dosing information as recorded on the RTX administration log on the eCRF and the actual treatment received as per IxRS. Exposure to RTX will not include RTX given as rescue, which will be analyzed separately.

MMF exposure data will be determined using the dosing information as recorded on the MMF administration log on the eCRF and the actual treatment received as per IxRS.

Exposure to MMF will be calculated as:

- date of the last MMF administration – date of the first MMF administration + 1

Exposure to MMF will not include MMF given as rescue, which will be analyzed separately.

The total cumulative dose will be calculated by summing the total daily dose over the treatment duration. Average daily dose will be calculated as:

- total cumulative dose ÷ treatment duration

Rituximab—F. Hoffmann-La Roche Ltd
30/Statistical Analysis Plan WA29330

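### The follow-up SAP borrows flare and steroid rules whose end dates fall before follow-up starts: as written, the flare offset holds no follow-up time and open-ended final steroid records stop at Week 52 or withdrawal

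*SAP*

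**What the plan says.** **Flares.** Follow-up SAP 3.7.1.3 consists of one cross-reference: "The total number of flares occurring during the SFU period will be summarized and analyzed as described in the primary SAP, Section 4.7.2.2". Primary SAP 4.7.2.2 fits a Poisson model with the log of each patient's "duration in study as an offset variable" and reports a rate ratio, 95% confidence interval and p-value. It sets exposure as "the duration from Day 1 to the earliest of the following: early withdrawal, receipt of rescue, Week 52 visit".

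**Steroids.** Follow-up SAP 3.7.1.1 summarizes cumulative dose and days on oral corticosteroids over follow-up, and ends: "See primary SAP, Section 4.7.2.1 for Data Handling for Oral Corticosteroids". In primary SAP 4.7.2.1 a missing or ongoing "final end date will be imputed with the exposure date". The only definition of that date is in primary SAP 4.9.1, under rituximab exposure: "exposure date is the earliest of the following", followed by the Week 52 visit (at latest Day 364+10) and early withdrawal.

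**Start of follow-up.** Follow-up SAP 3.2 starts the period at the earlier of Day 375+1 and the day after early treatment discontinuation. Section 3.4 defines a per-patient SFU duration, from the SFU start day to the last available SFU assessment, but only as a study-conduct summary.

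**The concern.** Both borrowed rules end on a date that precedes the period being analyzed, and the follow-up SAP replaces neither.

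For flares, events from one period would be divided by time from another. The error depends on how long the patient stayed on treatment, so it differs between arms if early withdrawal does. Protocol 3.1.1 sends treatment failures before Week 12 to an early withdrawal visit and then into follow-up. They fall outside the rescue population, which follow-up SAP 3.1 limits to Week 12 to Week 52, so the exclusion of rescue patients in 3.2.1 does not remove them. The patients with the shortest offsets therefore stay in the model.

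For steroids, a patient still taking prednisone at last contact is the natural case of an ongoing final record, and that is the record the rule closes too early.

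**Working it through.** The plan gives no figure of its own here, so the check applies the borrowed rules to the dates.

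**1. Flare offset, one patient.** Inputs: follow-up of 48 weeks (follow-up SAP section 1), taken as complete; offset equal to treatment-period weeks T, with T = 52 for a completer (primary SAP 4.7.2.2). Multiplier on the rate = 48/T. One flare in 48 weeks is correctly 52/48 = 1.08 per patient-year; as written it becomes 52/T.

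| Patient | T (weeks) | 48/T | Rate as written, per patient-year |
|---|---|---|---|
| Completer | 52 | 0.92 | 1.00 |
| Withdrawn Week 24 | 24 | 2.0 | 2.17 |
| Withdrawn Week 12 | 12 | 4.0 | 4.33 |
| Withdrawn Week 8 | 8 | 6.0 | 6.50 |

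**2. Flare rate ratio, equal true rates.** Let a proportion w of an arm withdraw at week T and the rest complete. Mean offset E = w × T + (1 − w) × 52. Flares per patient are the same in both arms, so the crude rate ratio A/B = E(B)/E(A). The withdrawal proportions and times are assumptions.

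| Withdrawal A v B | Week | E(A) | E(B) | Ratio A/B |
|---|---|---|---|---|
| 10% v 10% | 12 | 48.0 | 48.0 | 1.00 |
| 10% v 20% | 12 | 48.0 | 44.0 | 0.92 |
| 10% v 30% | 12 | 48.0 | 40.0 | 0.83 |
| 10% v 20% | 24 | 49.2 | 46.4 | 0.94 |
| 10% v 30% | 24 | 49.2 | 43.6 | 0.89 |
| 5% v 20% | 8 | 49.8 | 43.2 | 0.87 |

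The arm with fewer early withdrawals looks better. If the imbalance ran the other way, the ratios would invert. These are unadjusted ratios; the model's covariates could shift them somewhat.

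**3. Another reading of the offset.** If the offset is taken as all time from Day 1 to the end of follow-up, a completer has 52 + 48 = 100 weeks and a Week 8 withdrawal 8 + 48 = 56. With 5% v 20% withdrawn at Week 8: E(A) = 0.95 × 100 + 0.05 × 56 = 97.8; E(B) = 0.80 × 100 + 0.20 × 56 = 91.2; ratio 0.93. The distortion is smaller but remains.

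**4. Steroid end date.** SFU days counted for an open final record = max(0, imputed end − SFU start + 1).

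- Completer: imputed end at latest Day 364 + 10 = 374; SFU start Day 375 + 1 = 376; max(0, 374 − 376 + 1) = 0 days.
- Treatment stopped and patient withdrawn on day d: imputed end d, SFU start d + 1, so 0 days. If treatment stopped before the withdrawal date, a few days could count.
- Record that began in follow-up: its imputed end precedes its start. No rule covers that, so the result is undefined.
- Record with a real stop date in follow-up: counted normally.

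Size, for one open record at a constant assumed dose over 48 × 7 = 336 days: 2.5 mg/day loses 840 mg, 5 mg/day 1,680 mg, 10 mg/day 3,360 mg and 20 mg/day 6,720 mg.

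**The case against.** The best defence is that section 3.7.1.3 borrows a method and already restricts the count to flares in follow-up. A sensible programmer would then use follow-up time as the time base, and section 3.4 supplies it. Section 3.8 calls the data handling similar to the primary analysis, not identical. This may well be what was meant. But section 3.4 never names its duration as the offset, and 4.7.2.2 states an explicit exposure period, so the written rule gives the wrong denominator. Where SFU-specific rules were needed for visit windows, the follow-up SAP wrote them (section 3.3).

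On steroids, section 3.7.1.1 itself says all available data in each visit interval are used, up to withdrawal. That pulls against closing a record before follow-up starts. It does not redefine the exposure date, so the two texts conflict and should be reconciled. Primary SAP 4.7.2.1 also commits to resolving missing data before database lock, which should reduce missing dates but does not help a record that is truly ongoing.

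A reader might infer that follow-up steroid use as a whole is set to zero. The documents do not support that: each dose has its own start and stop dates, and only the final record is exposed, and only when its end date is missing or ongoing. A reader might also infer a bias toward rituximab. That needs an imbalance in early withdrawal, for which the documents give no figures. The factors also assume a full follow-up, whereas patients who withdraw consent are not followed (protocol 4.6.1).

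**Conclusion.** The point stands as a defect in the written rules. Followed literally, the follow-up flare model divides by time containing no follow-up, with factors from 0.92 for completers to 6 for a Week 8 withdrawal. With equal true rates the effect on the rate ratio is nil under balanced withdrawal and about 0.83 to 0.94 under the imbalances assumed above. The steroid defect is narrower: essentially no follow-up days for an open final record that began before follow-up, and an invalid interval for one that began during it.

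Everything affected sits under exploratory analyses (follow-up SAP 3.7). The primary endpoint and the fixed-sequence tests in primary SAP 4.7 do not depend on it. The flare model would still produce a rate ratio and p-value for the final report, so the rule should be corrected.

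**What to change.** - **Follow-up SAP 3.7.1.3:** state that the exposure period and offset are the SFU duration defined in section 3.4 (SFU start day to last available SFU assessment), replacing the exposure period in primary SAP 4.7.2.2.
- **Follow-up SAP 3.7.1.1:** state that a missing or ongoing final steroid end date is imputed with the last SFU assessment or SFU withdrawal date, instead of the primary SAP exposure date.

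The cost is two sentences before the final database lock, with no new data and no change to any confirmatory analysis. The same edit could align the Week 52 cut-off, which is Day 364+10 (374) in primary SAP 4.5 and 4.9.1 but Day 375 and Day 365+10 in follow-up SAP 3.2.

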3.7.1.4 Dermatology Life Quality Index

The Dermatology Life Quality Index (DLQI) is a validated patient-reported outcome. (See primary SAP, Section 4.7.2.5 for more details)

The absolute value (DLQI score) at each visit will be summarized descriptively using observed data.

3.7.1.5 Skindex-29

The Skindex-29 is a health-related quality of life (HRQoL) measure evaluating the impact of patient's dermatologic condition over the previous 4 weeks (See primary SAP, Section 4.7.3.9 for more details).

The Skindex-29 score will be summarized by visit and treatment group.

Each scale score is the mean of the items in that scale (domain). The overall score is the mean for the 29 items, i.e., excluding item 18.

The overall (global) score will be set to missing if more than 25% of the responses are missing.

3.7.1.6 Patient Global Impression of Change

The Patient Global Impression of Change (PGIC) is a measure of perceived change in PV symptoms as assessed by the patient (See primary SAP, Section 4.7.3.2 for more details).

The PGIC categories will be summarized by visit.

3.7.1.7 Clinician Global Impression of Change

The CGIC is a measure of perceived change in PV symptoms as assessed by the clinician (See primary SAP, Section 4.7.2.6 for more details).

The CGIC categories will be summarized by visit.

3.8 DATA HANDLING METHODS

Data handling methods are similar to the primary analysis (See primary SAP, Section 4.10).

- ^g The DLQI, PGIC, and Skindex-29 should be completed before all other assessments during the study visit and prior to providing patient with any disease status information. The CGIC, where possible, should be completed prior to the completion of other non-PRO study assessments.
- ^h To be captured on the eCRF.

Handling and Reporting of Laboratory Safety Data

This document describes methods used to standardize laboratory safety data for analysis and reporting purposes and presents for laboratory parameters that are frequently assessed in Roche/Genentech studies the range of values and changes from baseline for each laboratory test beyond which a value might be clinically relevant.

Standardization Methods

In clinical trials, samples for a particular laboratory parameter may be analyzed by several laboratories often using different methods. This can result in values being reported in different units with different reference ranges. Thus, to make the values comparable for analysis and reporting purposes, the following standardization process is applied to the data.

Conversion of values to Système International (SI) units

Where applicable, laboratory test values were converted from the investigator reported units to Système International (SI) units.

Transformation of data

For those tests that use common methodologies, a 'Roche Standard Reference Range' (adopted from the New England Journal of Medicine [[Kratz and Lewandrowski 1998](#), [Kratz et al. 2004](#)]) was applied since their normal ranges show only slight variation between different laboratories. For other tests where different methodologies are used between laboratories, and thus the reference ranges differ widely, values were linearly transformed to a 'Roche Standard Reference Range' before analysis and reporting using the following formula ([Smith and Givens 1993](#)):

(1)

$$R_T = S_L + [(R_U - I_L) / (I_H - I_L)] * (S_H - S_L)$$

R_T	transformed value
R_U	untransformed value
I_L, I_H	investigator limits, low and high
S_L, S_H	reference limits, low and high

Note: Values for females (where there are sex-dependent reference ranges) were transformed to the male reference range by replacing I_L, I_H by the reference limits for females, and S_L, S_H by the reference limits for males.

This linear transformation did not affect the relative position of a value to its reference range. For example, if an untransformed value was above the investigator's range, the transformed value was also above the Roche Standard Reference Range.

In cases where the transformed values could be negative, as could happen for low values where the lower limit of the reference range is zero or nearly zero, but the lower limit of the investigator range was markedly greater than zero, the investigator lower limit was replaced by zero for the transformation. This was considered to be clinically justifiable for tests where no abnormal pathology is evident at low values.

NOTE: For simplicity in technical implementation, standard reference ranges were expressed in the format “lower limit–upper limit” regardless of whether the actual limits were included in the published range (in some cases the reference ranges were one-sided).

Examples:

- Creatinine – Published reference range was <133 ($\mu\text{mol/L}$); implemented reference range was 0–133. A value equal to 133 was not flagged as high (outside the reference range).
- HDL Cholesterol -- Published reference range was ≥ 1.03 and <1.55 (mmol/L); implemented reference range was 1.03–1.55. A value equal to 1.55 was not flagged as high.

Marked Laboratory Test Value Abnormalities

For each laboratory parameter, a Marked Reference Range which was wider than the Roche Standard Reference Range was defined, above and/or below which a value was considered to be potentially clinically relevant. In addition, for each laboratory test, a percentage change, as an increase or decrease from the baseline value, was defined which represented a clinically relevant change from baseline. The ranges used to define a Marked Abnormality and the required change from baseline are shown in [Table 1](#).

A Marked Abnormality was therefore defined as a test result:

- which is outside of the Marked Reference Range,
- AND**
- which also represents a clinically relevant change from baseline of at least the designated amount during, or within a specified window after the end of, trial treatment (e.g., 30 days)

If the baseline value was zero and the percentage increase from baseline could not be calculated, the second condition was ignored (conservative approach).

Baseline was defined as the last valid value within a window specified by the project team (e.g., 30 days) before starting trial treatment. If no baseline was available, then the midpoint of the Standard Reference Range was used.

For crossover studies or parallel studies where treatment interruption longer than a specified period is of clinical significance: In general, if the wash-out interval was sufficient between 2 consecutive treatment periods, the user could derive a new baseline for the later of the 2 consecutive periods, as agreed within the project team.

NOTE: For calculating means and mean changes over time, missing values were not included. If no baseline was available, no change from baseline was calculated.

Table 1 Overview of Laboratory Parameters for Safety Reporting

Laboratory Test Class Laboratory Test	Specimen	SI Unit	Significant Decimals	Standard Reference Range ^{f, g, h}	Marked Reference Range	Direction of Change	Clinically Relevant Change from Baseline
HEMATOLOGY							
Hematocrit (PARAMCD = HCRIT)	Blood	fraction of 1	2	M 0.41–0.53 F 0.36–0.46 ^a	0.31–0.56	Increase Decrease	≥15% ≥15%
Hemoglobin (PARAMCD = HGB)	Blood	g/L	0	M 135–175 F 120–160 ^a	110–200	Increase Decrease	≥15% ≥15%
Leukocytes (WBC) (PARAMCD = WBC)	Blood	10 ⁹ /L	1	4.5–11.0	3.0–18.0	Increase Decrease	≥30% ≥30%
Platelets (PARAMCD = PLATE)	Blood	10 ⁹ /L	0	150–350	100–550	Increase Decrease	≥50% ≥30%
Mean corpuscular hemoglobin (MCH) (PARAMCD = MCH)	Blood	pgl	1	26.0–34.0	21.2–40.2	Increase Decrease	≥15% ≥15%
Mean corpuscular hemoglobin concentration (MCHC) (PARAMCD = MCHC)	Blood	g/L	0	310–370	260–430	Increase Decrease	≥15% ≥15%
Mean corpuscular volume (MCV) (PARAMCD = MCV)	Blood	fL	0	80–100	66–115	Increase Decrease	≥15% ≥15%
Erythrocytes (RBC) (PARAMCD = RBC)	Blood	10 ¹² /L	2	M 4.50–5.90 F 4.00–5.20 ^a	3.80–6.10	Increase Decrease	≥15% ≥15%

Laboratory Test Class Laboratory Test	Specimen	SI Unit	Significant Decimals	Standard Reference Range ^{f, g, h}	Marked Reference Range	Direction of Change	Clinically Relevant Change from Baseline
DIFFERENTIALSⁱ							
Bands (PARAMCD = BANDS)	Blood	10 ⁹ /L	2	0–0.70	0–1.40	Increase	≥30%
Bands (PARAMCD = BANDSF)	Blood	fraction of 1	2	0–0.10	0–0.15	Increase	≥30%
Basophils (PARAMCD = BASOS)	Blood	10 ⁹ /L	2	0–0.20	0–0.40	Increase	≥100%
Basophils (PARAMCD = BASOSF)	Blood	fraction of 1	2	0–0.03	0–0.06	Increase	≥100%
Lymphocytes (PARAMCD = LYMPH)	Blood	10 ⁹ /L	2	1.00–4.80	0.70–7.60	Increase Decrease	≥30% ≥30%
Lymphocytes (PARAMCD = LYMPHF)	Blood	fraction of 1	2	0.22–0.44	0.10–0.72	Increase Decrease	≥30% ≥30%
Monocytes (PARAMCD = MONOS)	Blood	10 ⁹ /L	2	0–0.80	0–1.70	Increase	≥100%
Monocytes (PARAMCD = MONOSF)	Blood	fraction of 1	2	0.04–0.11	0–0.22	Increase	≥100%
Neutrophils (PARAMCD = NEUTR)	Blood	10 ⁹ /L	2	1.80–7.70	1.50–9.25	Increase Decrease	≥20% ≥20%
Neutrophils (PARAMCD = NEUTRF)	Blood	fraction of 1	2	0.40–0.70	0.37–0.90	Increase Decrease	≥20% ≥20%
Eosinophils (PARAMCD = EOSIN)	Blood	10 ⁹ /L	2	0–0.45	0–0.90	Increase	≥100%
Eosinophils (PARAMCD = EOSINF)	Blood	fraction of 1	2	0–0.08	0–0.16	Increase	≥100%

Laboratory Test Class Laboratory Test	Specimen	SI Unit	Significant Decimals	Standard Reference Range ^{f, g, h}	Marked Reference Range	Direction of Change	Clinically Relevant Change from Baseline
COAGULATION							
Prothrombin Time, normalized ratio (PTINR) (PARAMCD = PTINR)	Plasma	fraction of 1	2	0.70–1.30	≤2.00	Increase	≥30%
Partial Thromboplastin Time, activated (PTT) (PARAMCD = PTT)	Plasma	sec	1	22.1–34.1	0–45	Increase	≥40%
Fibrinogen (PARAMCD = FIB)	Plasma	g/L	2	1.50–4.00 ^b	≥1.30	Decrease	≥30%
HEART FUNCTION							
Lactate Dehydrogenase (PARAMCD = LDH)	Blood	U/L	0	0–190 ^c	0–420	Increase	≥50%
Creatine Kinase (CPK) total (PARAMCD = CPK)	Blood	U/L	0	M 60–400 ^b F 40–150 ^a	≤800	Increase	≥50%
CPK (MB Fraction) (PARAMCD = CPKMB)	Blood	μg/L	0	0–7 ^c	0–7	Increase	>0
LIVER FUNCTION							
AST (SGOT) (PARAMCD = AST)	Blood	U/L	0	0–35 ^c	0–80	Increase	≥50%
ALT (SGPT) (PARAMCD = ALT)	Blood	U/L	0	0–35 ^c	0–110	Increase	≥50%
Alkaline Phosphatase (PARAMCD = ALKPH)	Blood	U/L	0	0–120 ^c	0–220	Increase	≥50%
Total Bilirubin (PARAMCD = TBILI)	Blood	μmol/L	1	0–17.0 ^c	0–34.0	Increase	≥75%
Direct bilirubin (PARAMCD = DBILI)	Blood	μmol/L	1	0–5.1 ^c	0–14.0	Increase	≥75%

Laboratory Test Class Laboratory Test	Specimen	SI Unit	Significant Decimals	Standard Reference Range ^{f, g, h}	Marked Reference Range	Direction of Change	Clinically Relevant Change from Baseline
Gamma Glutamyl Transferase (PARAMCD = GGT)	Blood	U/L	0	0–94 ^c	0–190	Increase	≥50%
RENAL FUNCTION							
Blood Urea Nitrogen (BUN) (PARAMCD = BUN)	Blood	mmol/L	1	3.6–7.1	0–14.3	Increase	≥50%
Creatinine (PARAMCD = CREATN)	Blood	μmol/L	0	0–133	0–154	Increase	≥50%
THYROID FUNCTION							
Triiodothyronine (T3) (PARAMCD = T3)	Blood	nmol/L	2	0.92–2.78	0.74–3.30	Increase Decrease	≥20% ≥20%
Thyroxine (T4) (PARAMCD = T4)	Blood	nmol/L	0	58–140	30–164	Increase Decrease	≥20% ≥20%
Free T4 (PARAMCD = T4FREE)	Blood	pmol/L	0	10–36	5–40	Increase Decrease	≥20% ≥20%
Thyroid-Stimulating Hormone (TSH) (PARAMCD = TSH)	Blood	mU/L	1	0–5.0 ^c	0–10.0	Increase	≥30%
PROTEIN							
Albumin (PARAMCD = ALBUM)	Blood	g/L	1	35.0–55.0	≥30	Decrease	≥20%
Total Protein (PARAMCD = TPROT)	Blood	g/L	0	55–80	50–87	Increase Decrease	≥20% ≥20%
LIPID CHEMISTRY							
Triglycerides (PARAMCD = TRIG)	Blood	mmol/L	2	0–1.80	0–2.83	Increase	≥100%
Cholesterol	Blood	mmol/L	2	0–6.18	0–8.30	Increase	≥30%

Laboratory Test Class Laboratory Test	Specimen	SI Unit	Significant Decimals	Standard Reference Range ^{f, g, h}	Marked Reference Range	Direction of Change	Clinically Relevant Change from Baseline
(PARAMCD = CHOLES)							
LDL-Cholesterol (PARAMCD = LDL)	Blood	mmol/L	2	0–4.13	0–5.4	Increase	≥30%
HDL-Cholesterol (PARAMCD = HDL)	Blood	mmol/L	2	1.03–1.55	≥0.65	Decrease	≥30%
ELECTROLYTES							
Chloride (PARAMCD = CHLOR)	Blood	mmol/L	0	98–106	95–115	Increase Decrease	≥7% ≥7%
Potassium (PARAMCD = POTAS)	Blood	mmol/L	1	3.5–5.0	2.9–5.8	Increase Decrease	≥20% ≥20%
Sodium (PARAMCD =SODIUM)	Blood	mmol/L	0	136–145	130–150	Increase Decrease	≥7% ≥7%
Bicarbonate (PARAMCD = BICARB)	Blood	mmol/L	0	21–28	17–30	Increase Decrease	≥20% ≥20%
MISCELLANEOUS							
Calcium (PARAMCD = CALCUM)	Blood	mmol/L	2	2.20–2.60	2.00–2.90	Increase Decrease	≥10% ≥10%
Phosphorus inorganic (PARAMCD = PHOSAT)	Blood	mmol/L	2	1.00–1.40	0.75–1.60	Increase Decrease	≥30% ≥30%
Blood Glucose (fasting) (PARAMCD = FASTGL)	Blood	mmol/L	2	4.20–6.40	2.80–11.10	Increase Decrease	≥75% ≥75%
Uric Acid (PARAMCD = URACID)	Blood	μmol/L	0	M 150–480 F 90–360 ^a	0–600	Increase	≥50%

Laboratory Test Class Laboratory Test	Specimen	SI Unit	Significant Decimals	Standard Reference Range ^{f, g, h}	Marked Reference Range	Direction of Change	Clinically Relevant Change from Baseline
URINALYSIS MICROSCOPIC^d							
Urinary spec. gravity ^e (PARAMCD =USG)	Urine	No unit	3	1.001–1.035	not defined	not defined	not defined

NOTE: Laboratory tests in bold are proposed as the minimal standard. All other tests are optional.
 
^a For reporting and analysing, the data for females are linearly transformed to the Reference Range for males according to formula (1).
 
^b For reporting and analyzing, the data are linearly transformed to the Reference Range according to formula (1).
 
^c For reporting and analysing, the data are linearly transformed to the Reference Range according to formula (1). To prevent transformed values becoming negative, the investigator lower limit is replaced by zero.
 
^d To be done if dipstick is positive and microscopic examination needed for specific quantitation/confirmation.
 
^e Specific gravity is a measurement of solute load in the urine. It is increased markedly by both proteinuria and glycosuria. A value >1.030 in the absence of proteinuria or glycosuria is most commonly caused by radiographic contrast. In volume depletion specific gravity is usually >1.020. A fixed value of 1.010 (isosthenuria) is characteristic of chronic renal impairment. A fixed value of 1.000–1.005 occurs in diabetes insipidus. Specific gravity has an important influence on urine microscopy because cells lyse more rapidly in dilute urine, which may lead to considerable inaccuracies in quantitation of cells. Cells swell and rupture in dilute urine and shrink in concentrate urine. Casts are rarely seen at low urine osmolality (Johnson and Feehally 2000). Conclusion: increase or decrease in urine specific gravity clinically relevant in context with other parameters from urinalysis.
 
^f Kratz and Lewandrowski 1998.
 
^g New England Journal of Medicine 1992 SI conversion guide.
 
^h Kratz et al. 2004.
 
ⁱ Harrison's Textbook of Internal Medicine.
							

References

Harrison's Textbook of Internal Medicine. Absolute Values of Differentials

New England Journal of Medicine. 1992 SI conversion guide

